*Note: NuvaRing is the only medication that will be included in the exclusion criteria. While we will ask all participants to provide a list of medical conditions they have and a list of medications they are currently taking, these will be for the purposes of data analysis, and to account for possible confounders of our data.

*Note: patients do not have to be symptom-free to participate in this study. However, as stated below, if they receive antibiotic/antifungal treatment prior to starting the study, we will ask them to wait 10 days after the completion of the treatment before they collect their first swab, in order to allow for the restoration of their baseline bacterial flora.

3. Vulnerable subjects:

N/A. Pregnancy is listed as an exclusion criteria, and no minors or incarcerated persons will be included in this study.

Section III: Methods and Procedures

1. Study design and methods

This is a single center, prospective trial, which comprises of a pre-post study design will be looking at the vaginal microbiome makeup of participants before and after a four-week course of Phexxi. The primary outcomes will be an increase in lactic acid-forming lactobacilli, as well as a decrease in patient-reported symptoms of vulvovaginitis.

This study will be based at the Queen's Medical Center (QMC), [name]. Eligible patients will be approached by participating clinicians (all doctors providing care at the 1004 clinic, as delineated in the LOA form) to assess interest in study participation.. The principal investigator will review the weekly schedule for the 1004 clinic and alert the attending physicians of patients who may be eligible for the study based on chart review. A HIPAA waiver will be required for this stage of recruitment, as the principal investigator would otherwise not be accessing these patient's charts. The attending physician staffing the 1004 clinic will ask the flagged patients if they are interested in learning about the study and review general study objectives with patients. If the patient is interested in participating, the research associates will approach the patient to more thoroughly screen, then conduct the informed consent process. Informed consent will be collected from every participant prior to the start of the study.

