After obtaining informed consent, the research team will review standardized instructions for using the study medication with the patient and the research associate will provide a take-home kit including all of the study materials, including instructions for collecting each swab (Appendix A) and for returning the samples. Samples will be self-collected by participants at their home at intervals specified in the study instructions. All materials provided to the patient will be pre-labeled with their study ID, protecting each participant's PHI. No collections will take place in-clinic. These materials include all surveys, patient's diary, and all swab vials.

All vaginal swabs must be frozen within 48 hours of collection. As such, the participants will be asked to send their samples within 24 hours in order to give adequate time for delivery to the storage facility and be asked to collect their specimens between Sunday and Thursday so samples can reach the facility during business hours. Freezing will occur at the research site. Each patient's study kit will include a prepaid shipping envelope, which the participant can use to mail or drive their specimen to the research team who will then place it in the freezer until it is ready for analysis.

The first phase of the study will include an assessment and classification of patients' vaginal microbiome prior to receipt of the intervention. To get the best representation of the participant's baseline microbiome, the participant will be asked to collect their baseline swab no sooner than 10 days after menses, as menses-induced changes in the microbiome have been shown to resolve after this time¹². For similar reasons, if participants are being treated with an acute course of antibiotics or antifungals at the time of recruitment, they will be asked to wait 10 days after the completion of their medication course before collecting their baseline swab. There will be two additional time points for collection: collection 2) at the end of the 30 day intervention, and collection 3) 30 days after completion of the intervention.

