The intervention will take place on a rolling basis, as patient participation will have no bearing on other participants. The intervention itself will take place over thirty days. 8 pre-filled vaginal inserters with vaginal gel, will be provided to each of the participants with verbal and written instructions for application. Patients will be instructed to use Phexxi twice per week, on the same days every week. Throughout the 30 days, participants will also be asked to keep a diary of events (Appendix E) occurring when they used the product, such as intercourse or menses, as well as record any symptoms or side effects they noticed when using the product. The diary can be sent back with the second specimen vial. Disposal of the product may be done in a regular waste basket.

Approximately 30 days after completion of the intervention, participants will receive an email reminder to collect and send a third collection swab in (Appendix G) for analysis. This email will also include the link for the third and final set of surveys (B and C).

2. Data analysis and monitoring (include adverse event reporting procedures)

The pre-and post-intervention results will be compared with the subjects to serve as their own controls in this pilot study. To assess for the primary outcomes, each bacteria identified in the NextGen analyses of the composition of the pre-intervention microbiome sampling will be individually named, then classified as either “lactic acid-forming (LAF)” or “not lactic acid-forming (NLF)”. This will allow us to identify which CST each participant falls under prior to the study, and to assess if they can be classified under a different CST at the end of the study. It also allows us to conduct an independent t-test to test for significance between two variables (LAF/NLF) pre and post-intervention.

Demographic data will be collected from patient surveys. Demographic information to be collected will include age, ethnicity, number of reported vaginal yeast infections or BV infections in the last year, type of contraception used, type of diet, and medical comorbidities/current medications. This demographic information will allow us to perform a multiple regression analysis on our data set to account for confounding factors in our study population.

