Patients of the 1004 clinic who have been seen two or more times in the past year for recurring symptoms of vulvovaginitis will be screened for this study. In addition, informational posters will be put up in clinic offices in order to invite patients who are interested in the study to undergo screening for suitability of participation.

2. Process of consent:

Each week, the principal investigator will review the records of patients scheduled for appointments in the 1004 clinic for eligibility. These patients will be informed about the study during their visit, and if interested, a research team member will perform a thorough analysis for eligibility. Researcher or research associate will approach patients who are screened as eligible to enroll in the study. A standard, IRB-approved consent form will be used. The consent form will be reviewed, explaining the nature and purpose of the study, intervention and tasks associated with participating, as well as all risks and benefits associated with participation. Research associates can answer questions about the study and complete informed consent. If questions are outside of research associates' scope, then physicians will be available to answer these questions. If enrolled, patients will be provided a signed copy of the consent form.

3. Subject capacity assessment procedures: Not applicable

4. Subject/Representative comprehension:

Patient must be able to understand and communicate effectively in English. As part of obtaining informed consent, patients must be able to demonstrate comprehension of the risks and benefits of study to the researcher. If they are unable to do so using basic English, they will not be deemed appropriate for participation in this study.

5. Debriefing procedures for non-disclosed information (if applicable): not applicable
6. Documentation of consent/assent:

An IRB-approved consent form will be used to document consent. Subjects will be provided with a copy of the consent form. A copy of the signed consent form will be scanned into the subject's medical record.

7. Costs to the subject: No monetary cost will be incurred by the subject, unless the patient develops side effects to the study drug and needs to seek medical attention for these side effects. As stated above, if this occurs, the patient will be responsible for using their insurance plan to cover the costs incurred.

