Appendix B Patient demographic survey

Demographic Survey

Subject ID:

1: What is your age?:

2: What is your race?

3. Are you Hispanic/Latinx?

4.: How many yeast infections or episodes of bacterial vaginosis (BV) have you had in the last year?

5: Are you on any kind of birth control? If yes, what kind?

6: In the next portion, please describe what kinds of food you normally eat in a typical day. In addition to meals, please include snacks. If you are currently on a specific type of diet, please state that here.

Breakfast

Lunch

Dinner

Other

7 What other medical conditions have you been diagnosed with? If none, please write, "none".

8: Please list any medications/supplements you are currently taking. If none, please write, "none".

Appendix C. Survey to assess vulvovaginitis symptoms. Modified version of the Vulvovaginitis Symptom Questionnaire (VSQ)

During the past week, have you been bothered by:

1. Your vulva itching? 0 No 1 Yes

2. Your vulva burning or stinging? 0 No 1 Yes

3. Your vulva hurting? 0 No 1 Yes

4. Your vulva being irritated? 0 No 1 Yes

5. Your vulva being dry? 0 No 1 Yes

6. Discharge from your vulva or vagina? 0 No 1 Yes

7. Odor from your vulva or vagina? 0 No 1 Yes

8. Worry about your vulvar symptoms? (for example, that it will spread, get worse, scar, etc.) 0 No 1 Yes

9. The appearance of your vulva? 0 No 1 Yes

10. Frustration about your vulvar symptoms? 0 No 1 Yes

11. Embarrassment about your vulvar symptoms? 0 No 1 Yes

- 12. The effects of your vulvar symptoms on your interactions with others? 0 No 1 Yes
- 13. The effects of your vulvar symptoms on your desire to be with people? 0 No 1 Yes
- 14. Your vulvar symptoms making it hard to show affection? 0 No 1 Yes
- 15. The effects of your vulvar symptoms on your daily activities? 0 No 1 Yes
- 16. Your vulvar symptoms affecting your desire to be intimate? 0 No 1 Yes
- 17. Are you currently sexually active with a partner?
 No → Thank you. You are done with this questionnaire. Yes → Please proceed with the next 4 questions
- 18. The effects of your vulvar symptoms on your sexual relationships? 0 No 1 Yes
- 19. Your vulvar symptoms causing pain during sexual activity? 0 No 1 Yes
- 20. Your vulvar symptoms causing dryness during sexual activity? 0 No 1 Yes
- 21. Your vulvar symptoms causing bleeding during sexual activity? 0 No 1 Yes

Please use the space below to list any vulvar/vaginal symptoms you are experiencing which have not already been listed.

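### The multiple regression on items recorded once at baseline cannot deliver the adjustment for confounding that the protocol claims, because in a one-arm paired comparison it leaves shared change over time in the result

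*Protocol*

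**What the plan says.** The design is one arm, before and after. Section III.2 states: "The pre-and post-intervention results will be compared with the subjects to serve as their own controls in this pilot study". Section I.1 frames the first primary outcome causally, asking whether use of the product brings about change in the microbiome.

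Section III.2 then lists the survey items: "age, ethnicity, number of reported vaginal yeast infections or BV infections in the last year, type of contraception used, type of diet", followed by comorbidities and current medications. It gives their purpose: "This demographic information will allow us to perform a multiple regression analysis on our data set to account for confounding factors in our study population". The note under the exclusion criteria in Section II.2 gives the same purpose for medical conditions and medications: "these will be for the purposes of data analysis, and to account for possible confounders of our data".

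Section III.1 places the survey (Appendix B) in the first phase, before the intervention. No repeat is stated. The test named in Section III.2 for lactic acid-forming against other bacteria, before and after, is an independent t-test. Section II.1 plans 20 women, raised to 22 for 10% exclusions and dropouts.

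**The concern.** A confounder has to be associated with the contrast being estimated. Here the contrast is after against before in the same woman. An item with one value per woman is identical on both sides, so in complete pairs it is not associated with that contrast. What competes with a gel effect is change over time that happens to everyone, and no item measured once at baseline carries information about that.

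The protocol's own recruitment makes such change plausible. Section V.1 screens women "seen two or more times in the past year for recurring symptoms of vulvovaginitis", and the note in Section II.2 adds that "patients do not have to be symptom-free to participate in this study". Women chosen for recent disease, some of them symptomatic at entry, may improve without treatment. Section III.1 also sets a minimum interval after menses for the baseline swab and states none for the two later swabs.

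At stake is the wording of the conclusion. A report that follows Section III.2 could call the change adjusted for confounding while the main alternative explanations remain in it. Readers would then trust the answer to a causal question more than a one-arm design allows.

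**Working it through.** **Inputs.** n = 20 (22 enrolled), from Section II.1. Six listed items, from Section III.2. The protocol gives no size for drift, recovery or the number recently treated, so those below are assumptions. All effects are in SD of the within-woman change.

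**The plan's own figure.** The pilot formula gives ln(1 − 0.95)/ln(1 − 0.15) = 18.43, so 19 against the stated 20; 20 × 1.10 = 22. This is close enough, and nothing below disputes it.

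**1. Adjusted mean equals raw mean.** Let d be a woman's change and x her baseline items, centred at their sample means. In the least-squares fit d = a + b·x, the intercept a is the sample mean of d, whatever b is. In simulation (n = 20, six covariates, drift 0.5, no gel effect, 4,000 datasets per setting) the largest difference between the two was 7e-16:

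| Variance of change truly explained by covariates | Raw mean | Adjusted mean | Ratio of 95% CI widths, adjusted/raw |
|---|---|---|---|
| 0% | 0.503 | 0.503 | 1.03 |
| 10% | 0.506 | 0.506 | 0.97 |
| 30% | 0.495 | 0.495 | 0.86 |

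The covariates alter the width of the interval and leave its centre where it was.

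**2. What shared drift does.** With no gel effect, the paired t-test at n = 20 (noncentral t, 19 df, noncentrality drift × √20) gives two-sided p<0.05 with these probabilities:

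| Assumed shared drift | Chance of p<0.05, unadjusted | Simulated, with six covariates |
|---|---|---|
| 0 | 5% | 5% |
| 0.25 | 19% | 20% |
| 0.5 | 56% | 59% |
| 0.8 | 92% | 93% |

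The last column is a separate simulation in which one covariate predicts the change. Adjustment gives no protection.

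**3. Recent treatment, a partial exception.** A baseline indicator for recent treatment modifies the change, and the fit can be read at the untreated level. Assume 8 of 20 women were recently treated and recover by 1 SD, with no gel effect. The raw change is 8/20 × 1 = 0.40, and the reading for women not recently treated is 0.00. With a drift of 0.5 as well, these become 0.90 and 0.50. Recovery is removed, drift is not.

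The data for this are not secured. Appendix B, question 8, reads "Please list any medications/supplements you are currently taking". It captures a course still under way, but one finished before the survey need not be recorded. Section III.1 says of women under acute treatment at recruitment that "they will be asked to wait 10 days after the completion of their medication course before collecting their baseline swab", so the team must know of some courses; no field in Appendix B asks for the end date.

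**4. When baseline items can matter.** Suppose 22 women give a baseline swab, 4 of them sit 1 unit lower, 2 of those 4 withdraw, and nobody changes (all assumed). The unpaired difference is −2/20 − (−4/22) = −0.100 + 0.182 = 0.08. Adjusting for the item returns about 0.00. Baseline items therefore help with selective loss in an unpaired comparison. They still do nothing about drift.

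**5. If all six items were entered with one term each (an assumption).** Residual df are 20 − 6 − 1 = 13, or 22 − 6 − 1 = 15. Expected R-squared with no true relation is 6/19 = 0.32 (5th to 95th percentile 0.10 to 0.57), or 6/21 = 0.29 with 22 women. The 95% CI half-width of a slope, per SD of the covariate, is about 0.50 with one term, 0.51 with two and 0.60 with six.

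**The case against.** **The sentence is loose, not false.** Section III.2 nowhere claims to remove natural course or regression to the mean, and the one-arm design is openly described. That is fair, and such pilots are accepted. But the sentence assigns the regression a task, and in complete pairs fixed items cannot perform it. The protocol states no limitation that would correct the impression.

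**Baseline items are not always irrelevant.** This stands. Section III.2 names an independent t-test, Section II.1 expects losses and Section IV.3 withdraws women who develop side effects. Where pairs are broken, fixed items can confound, and regression can help (step 4). A reader might infer that baseline covariates never matter in this trial; the protocol does not support that. What holds in either case is that they do not remove shared drift.

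**The sizes are invented.** Also fair. The protocol fixes neither the model nor any drift, and an analysis plan that is not shown may specify the terms. A reader might infer that a six-term model is planned; it is not stated. The equality in step 1 needs none of these sizes, and no later choice among items recorded once at baseline changes it.

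**Leaving out women with diary events could bias the result.** This stands for new medication. Appendix F lists mycotic infection (9.1%), urinary tract infection (9.0%) and bacterial vaginosis (8.4%) among reactions reported with the product. Medication begun after baseline may treat an infection that arose on the gel. If 4 of 20 women worsen by 1 SD and the rest do not change (assumed), the mean is −0.20; leaving those 4 out gives 0.00, which favours the gel.

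**Conclusion.** The point holds for complete pairs analysed as paired: fixed baseline items cannot confound the mean within-woman change, and regression on them leaves shared change over time untouched. With incomplete pairs or an unpaired test they can matter, but shared drift still remains. The equality of raw and adjusted means is exact. The drift, recovery, treated-number and six-term figures are illustrations under assumptions and say nothing about how large these effects are in this trial.

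Two stronger readings are tempting and not supported. One is that the regression distorts the estimate: the paired mean change is the same with and without it, and predictive covariates could even narrow the interval. The other is that the trial is invalid without a control arm: a one-arm pilot can describe change, and only the claim of adjustment goes beyond the design. The correction should be made because it affects how the primary result is interpreted.

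**What to change.** 1. In Section III.2, and for fixed items in the Section II.2 note, replace the claim of adjustment with wording such as: one or two baseline items named in advance (for example, episodes in the past year) will be used to explore whether the change differs between women. With slope half-widths near 0.5 SD, this is exploratory only.
2. Make the unadjusted paired within-woman change the main result. This also replaces the independent t-test in Section III.2, so it is a change of method and not only of wording.
3. State that change over time cannot be separated from a gel effect without a control group, and that the result will not be reported as adjusted for confounding.

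Optional: a sensitivity analysis leaving out women whose diary shows menses near the second swab, with the window fixed in advance. Section III.1 asks for events when the product was used, so a blank entry does not rule out menses, and this should be acknowledged. Do not exclude women for new medication after baseline. Examining treatment before baseline would need an added end-date field.

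Cost: items 1 and 3 are text; item 2 changes the test and needs no new data. The multi-covariate adjusted table is lost, as is any precision from predictive covariates; the point estimate of the paired mean change is unaffected. The optional analysis is less precise: the paired 95% CI half-width, t(0.975, n − 1)/√n, is 0.47 SD at 20 women, 0.53 at 16 and 0.64 at 12.

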Once received at the research site, samples will be stored in a specimen freezer at -80 degrees F until all specimens are received, at which point they will analyzed using NextGen sequencing, a DNA sequencing technology that will identify the genetic makeup of their specimens. This will be done to sequence the genome of the bacteria of the microbiome, not the patient's genetic material. The first phase of the study will also include a survey (Appendix B), which will collect demographic information from each participant, as well as assess patients' current acceptability of a vaginal gel for prophylactic use, their most bothersome symptoms, and how their quality of life is affected by recurrent vulvovaginitis. The specific information collected from each

participant can be found below in Data Analysis. The survey used to measure this will be the **Vulvovaginal Symptom Questionnaire (VSQ)**, which has been validated for the purposes stated above (Appendix C). There will also be an added space in the survey provided for open-ended answers and comments.

Measurement for primary outcomes will be done using two separate methods. In order to assess for the presence of lactic acid-forming organisms before and after the lactic acid gel intervention, NextGen DNA sequencing will be completed on self-collected samples submitted by participants. The analysis of these samples will be performed by [name], at an in-house lab run by the UH Maternal Fetal Medicine division. In order to assess for patient-experienced symptoms, **survey B (Appendix C) will be administered prior to, immediately after, and 30 days after intervention.**

In order to measure our secondary outcome, Survey C (Appendix D) will be administered at collection points 2 and 3.

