- a. There is minimal risk that the privacy of the patient's medical information could be breached.
- b. There is slight risk that participants could experience side effects from the intravaginal Phexxi, as listed in the drug information in Appendix F). However, as lactic acid is a substance that typically resides in the vagina, the likelihood of serious side effects from inserting it vaginally is low.

3. Protection against risk(s):

Please see Section III, #3 above regarding protection of patient's medical information. Regarding side effects of Phexxi, the patient will be adequately counseled on the side effect profile of the treatment, and instructed to discontinue the intervention if these side effects occur and are intolerable to the patient.

If participants develop side effects, the following will take place:

- The patient will be told to discontinue the study drug, and will be withdrawn from the study. This adverse event will be reported to the RIRC.

- If the patient marked on the ICF that they would like their primary Gyn provider to be notified in the case of an adverse event, the research team will send a secure chat message (through the EMR) the patient's primary provider.
- A follow-up visit will be scheduled with the patient to ensure that the unused study drug is returned to the research team
- The patient will be responsible for seeking care from their provider, and using their insurance plan to cover the costs of any treatment required.

4. Potential benefit(s) to the subject (direct medical benefit(s)):

The direct benefit to the subject includes potential prevention and resolution of their recurrent vulvovaginitis symptoms. Additionally, the Phexxi intravaginal gel is primarily used as a contraceptive agent, and thus if the treatment is used prior to intercourse, the patient will benefit from the contraceptive effects of the treatment.

5. Alternative to participation:

Declining participation will not affect patients' medical care, as patients will not be declined the standard of care treatment for BV or yeast infections, which are antibiotics or anti-fungal agents, respectively.

Section V: Subject Identification, and Consent/Assent

1. Method of subject identification and recruitment:

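### Section IV.3 ends study participation, not only gel use, when side effects occur: outcomes can be lost through intolerance, probably flattering satisfaction among completers, with a small symptom bias of uncertain sign

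*Protocol*

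**What the plan says.** Section IV.3 (Protection against risk(s)) deals with side effects in two steps. Its opening paragraph says women will be counselled and "instructed to discontinue the intervention if these side effects occur and are intolerable to the patient". A list then follows, introduced as applying when a participant has side effects, with no threshold of severity. Its first item is: "The patient will be told to discontinue the study drug, and will be withdrawn from the study". The event goes to the review committee and, if the woman has asked for it, her provider is told. The only later study contact described is for the drug: "A follow-up visit will be scheduled with the patient to ensure that the unused study drug is returned to the research team". On care, "The patient will be responsible for seeking care from their provider".

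The outcomes are scheduled in Section III.1. On symptoms, a primary outcome, "survey B (Appendix C) will be administered prior to, immediately after, and 30 days after intervention". Survey C, the secondary outcome of satisfaction and acceptability, is given only at the second and third collections. Swabs 2 and 3 are due at the end of the 30-day intervention and 30 days after its completion. Section III.2 compares each woman with herself before and after.

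Three other provisions bear on the point. The notes in Section II.2 state that "patients do not have to be symptom-free to participate in this study". Survey B (Appendix C) asks: "During the past week, have you been bothered by". During the 30 days women keep a diary in which they "record any symptoms or side effects they noticed when using the product", and it comes back with the second specimen.

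**The concern.** Stopping a drug and leaving a study are separate acts, and the rule joins them. Whether post-treatment data exist then depends on how the woman tolerated the gel, which is close to what two of the outcomes measure.

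For satisfaction the link is direct. A woman who stops early because of burning never rates the gel, so the reported ratings come from women who tolerated it.

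For symptoms the link is plausible but looser. Four of the ten reactions in Appendix F correspond to Survey B items: burning (18.0%), pruritus (14.5%), discharge (5.5%) and pain (2.1%). Two more, mycotic infection (9.1%) and bacterial vaginosis (8.4%), are the conditions the gel is meant to prevent.

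This is an affirmative rule in the protocol and not a detail left to an analysis plan. The consent pages are not in this copy, so the point rests on the stated rule and not on what consent may or may not say.

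**Working it through.** **The plan's own figures.** Section II.1 enrols 22, which is 20 × 1.10, with 10% allowed for all exclusions and dropouts. The protocol gives no rate of withdrawal for side effects. I assume w = 5%, and take 10% (the whole allowance) as a high value. An outer case, w = 18%, needs the broad trigger and carries over the burning rate from contraceptive use.

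**How many women.** Expected losses: 22 × 0.05 = 1.1 and 22 × 0.10 = 2.2. Chance of losing at least one: 1 − 0.95^22 = 0.68 and 1 − 0.90^22 = 0.90. The chance of losing none is therefore 32% or 10%. In the outer case, 22 × 0.18 = 4.0 women.

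**Model for the bias.** A woman is withdrawn if a latent score exceeds its 1 − w quantile z. That score has correlation r with a driver; r = 0.5-0.7 is assumed. If the driver has correlation c with the outcome, the completers' mean is shifted by −r·c·φ(z)/(1 − w) SD. The factor φ(z)/(1 − w) is 0.109, 0.195 and 0.320 at w = 5%, 10% and 18%.

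**Survey C.** Withdrawal falls on low raters, so the overstatement is r·φ(z)/(1 − w):
- w = 5%: 0.5 × 0.109 to 0.7 × 0.109 = 0.05-0.08 SD
- w = 10%: 0.5 × 0.195 to 0.7 × 0.195 = 0.10-0.14 SD

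As a bound, if withdrawn women would tick none of the 12 statements in Appendix D, the mean number ticked is overstated by 1/(1 − w) − 1, which is 5% or 11%.

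**Survey B change.** No test is named for it. I assume a paired t-test at one-sided 2.5%, no true change, and pre-post correlation ρ = 0.5. The change score then has SD √(2(1 − ρ)) = 1, and c for the post score is √((1 − ρ)/2) = 0.5. Negative values are spurious improvement. False-improvement rates are simulated (n = 22, 40,000 replicates per cell; 2.5% with no withdrawal). Ranges run over r = 0.5-0.7.

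| Withdrawal follows | c | Bias, w = 5% | Bias, w = 10% | False improvement, 5% / 10% |
|---|---|---|---|---|
| Post score | 0.5 | −0.03 to −0.04 | −0.05 to −0.07 | 3.4-3.5% / 4.1-4.7% |
| 75% post, 25% baseline | 0.277 | about −0.02 | −0.03 to −0.04 | about 3% / 3.3-3.5% |
| Equal weights | 0 | 0 | 0 | no bias |
| Baseline score | −0.5 | +0.03 to +0.04 | +0.05 to +0.07 | 1.7-1.9% / 1.3-1.6% |
| Change score | 1 | −0.05 to −0.08 | −0.10 to −0.14 | 4.1-5.0% / 6.0-8.3% |

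A rerun of the post, baseline and change cells agreed within about 0.3 percentage points. At w = 18% with the post score as driver, the bias is 0.5 × 0.5 × 0.320 to 0.7 × 0.5 × 0.320 = 0.08-0.11 SD, with 5-7% false improvement; with baseline as driver it reverses by the same amount.

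**Timing.** These figures treat every withdrawn woman as losing all post-treatment data. Collections are at home and no contact is scheduled during treatment. Side effects known only from the diary reach the team with swab 2, so that woman loses collection 3 only. The figures are therefore upper ones for a given w and r.

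**The case against.** The strongest opposing case is about size and certainty. With about 20 women, the standard error of a mean change is 1/√20 = 0.22 SD. A symptom bias of 0.027-0.068 SD is then about 12-30% of one standard error, in an uncontrolled pilot. That stands, and the point should not be sold on the symptom outcome.

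A reader might infer that the symptom result will be biased towards the gel. The protocol does not support that. Women may enter with symptoms; if the more symptomatic ones react and leave, the bias reverses. Survey B covers only the past week, so a woman who stopped in week 1 would, at collection 2, report on a week about three weeks off the gel. Nothing in the protocol favours one row of the table over another.

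A reader might also infer that satisfaction is certain to be inflated. It is not. No woman may be lost, and some Survey C statements ask whether use is possible or easy, which a woman with burning could still endorse.

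The two stopping sentences are partly an editorial matter. The list follows directly on the sentence about intolerable effects, and a 30-day side-effect diary makes little sense if any mild effect ends participation. So a loss of 18% is an outer case and not a forecast.

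Withdrawals are also visible, since each is reported as an adverse event. Counting them beside Survey C would help, but it does not supply the missing ratings.

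Finally, the hypothesis concerns regular use over a four-week course, so adding women with one or two doses alters the question. That is fair, and is why the fix reports both sets.

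**Conclusion.** The concern holds in a limited form and should be fixed. As written, Section IV.3 removes women from the study because of side effects. Those removed before collection 2 supply no Survey C rating and no post-treatment Survey B score or swab. That this data collection stops is inferred from the withdrawal and from the absence of any later collection step, which is the ordinary reading.

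If at least one woman is lost this way, completers' satisfaction is likely to favour the gel, by up to about 0.05-0.14 SD at 5-10% withdrawal. This assumes that side effects lower ratings.

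For symptom change the effect is small and its sign open: about 0.03-0.07 SD either way when withdrawal follows the post or the baseline score. It is larger, 0.05-0.14 SD, only if withdrawal follows the change itself. No direction is claimed for the microbiome. Withdrawal rates, correlations and drivers are all assumed; the protocol gives none of them.

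**What to change.** State in Section IV.3 that stopping the gel for side effects does not end study participation. Unless she withdraws consent, the woman completes swab 2 with Surveys B and C at day 30 from her first dose, and swab 3 with both surveys 30 days later. Early stoppers need these dates because collection 3 is now timed from completing the intervention. They should get the same email link to the third surveys and the same second $10 payment.

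Record antibiotic or antifungal use, with dates, through collection 3. Report Survey C and the pre-post symptom comparison for all enrolled women with data, and again for those who completed the course, flagging data collected after rescue treatment. Make the two stopping sentences agree; no view is taken here on which clinical rule is right. Adverse event reporting, provider notice and drug return are unchanged.

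The cost is a short change to protocol and consent wording. The take-home kit already includes the surveys and swab vials, a contact after stopping is already planned, and the diary has a place for new medications; the medication question must be repeated at collection 3. The downside is that some data will come from women with few doses or after rescue treatment, and women who stopped have up to two more swabs and survey sets to complete.
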